7	04/10/2020	
Section 7.4 and Section 8 – add language to clarify that the standard of care procedures in Section 8.1 should be followed for patients who are enrolled for retreatment.
 
Section 8.1 – clarified timing of procedures on the days of infusion.
 
Consent changes – added background information to retreatment consent and updated long term specimen storage language to state that samples will be under the control of GT BioPharma.
	Yes
8	05/18/2020	Study Schema, Section 7.2, and Section 10.3 – DLT assessments are protocol defined at Day 29. We recognized that our currently approved protocol has 2 different dates for assessment in the DLT section (Day 29 for non-hematologic and Day 42 for Hematologic assessment) which is incongruent. Thus, revised DLT assessments to clarify that hematological toxicity will be defined as lasting $\geq$ 29 days from start of cycle as all DLT assessments need to have the same timeline to be congruent with moving forward with subsequent patients at 29 days..	No
9	08/31/2020	
Section 7.1.5 and Section 7.5 – clarify that if after completing Block 1 and Block 2 patients with clear evidence of disease progression will discontinue treatment but will be fully evaluable for toxicity and efficacy
 
Section 7.1 and Section 9.6 – Update the drug preparation instructions to match the study's Pharmacy Manual
 
Section 12.1 – add the definition of evaluable and when to replace a patient to complete enrollment.
 
Other minor edits and clarifications
	No
10	10/05/2020	
Synopsis, Section 6.4 and Section 7.4 - clarify when re-treatment may be considered.
 
Section 10.6 – Delete [REDACTED] from the list of persons who receive participating sites event reports for initial review.
 
Section 10.7 – Clarify UMN's reporting flow to GTB and [REDACTED] for SAEs, remove link for MCC SAE reporting as process has changed and receiving report notification via [REDACTED].
 
Section 11.3 – Clarify that this study complies with the Masonic Cancer Data and Safety Monitoring Plan (DSMP) and add the link to the plan.
 
Section 11.5 – add ICH compliant record retention information.
 
Other minor edits and clarifications.
	No

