### **6.4 Inability to Begin Study Treatment**

If a patient is enrolled to the study, and is later found not able begin the study treatment, for whatever reason, the patient will be taken off study and treated at the physician's discretion. The Study Coordinator or designee will update [REDACTED] of the patient's non-treatment status. The patient will be replaced to fulfill enrollment requirements.

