### **7.2.2 Extended Component (Phase II)**

The treatment schedule is identical to the dose finding component. The extended component uses a Simon's MiniMax two-stage design for continued enrollment using the maximum tolerated dose (MTD) established during Phase I with monitoring guidelines to stop the study early for excessive toxicity.

In Stage 1, a total of 13 patients (including all treated at the MTD in part 1) will be enrolled. If 3 or more of these have clinical response the trial will continue to Stage 2. If the phase I component enrolls more than 13 patients at the MTD, the two-stage design will be adjusted with the given number of patients enrolled at the MTD.

In Stage 2, an additional 17 patients will be enrolled for a total of 30 patients treated at the MTD.

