## 12 Statistical Considerations

### 12.1 Study Design and Endpoints

This is a multisite Phase I/II study of GTB-3550 trispecific killer cell engager (TriKE) for the treatment of high risk MDS and relapsed AML. Once the MTD is identified, the objective will be to confirm safety and obtain preliminary estimates of efficacy as measured by the objective response, the **primary trial endpoint** as assessed between Day 21 and Day 42. For AML clinical response includes complete remission with or without hematologic or platelet recovery (CR, CRi or CRp) or partial response. For MDS clinical response includes complete remission, marrow CR (with incomplete peripheral blood count normalization), partial response or hematologic improvement (HI). For advanced systemic mastocytosis response is considered a decrease in mast cell burden in bone marrow or serum tryptase level by at least 30%.

All patients completing Block #1 will be evaluable for DLTs and toxicities. Patients who discontinue therapy prior to completion of both Block #1 and Block #2 will be replaced. Patients completing Block #1 and Block #2, but come off treatment for disease progression, will still be evaluable for efficacy and will not be replaced. If needed a subgroup of patients receiving all 3 blocks will also be evaluated for response as a secondary population. We expect that the number of patients coming off therapy after only completing block #1 will be minimal.

**Secondary trial endpoints** will include toxicity through Day 29 and overall survival (OS) at 6 months from 1st dose of study drug.

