## **Phase II Extension: Studying the efficacy of GTB-3550 TriKE for the endpoint of objective response:**

After completion of the dose finding trial, the final dose will be carried forward into an uncontrolled two-stage Phase II extension trial to confirm safety and make a preliminary determination of the activity level. For advanced MDS/AML, the lack of

defined effective alternative therapies precludes a control regimen for comparisons at this stage of testing. If the Phase I trial enrolls fewer than 14 patients at the MTD, we will employ a Simon's Minimax two-stage design with the possibility to discontinue after the 1st stage if the response rate is low.

- Stage 1: Enroll a total of 13 patients (including all treated at the MTD in Phase I). If 3 or more of these respond, the trial will continue to stage 2.
- Stage 2: Enroll an additional 17 patients. If 10 of 30 patients respond, GTB-3550 TriKE will be considered promising for further investigation.

If the Phase I trial enrolls more than 13 patients at the MTD, we will adjust the futility rule above for the two-stage design with the given number of patients enrolled at the MTD.

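### Section 12.1 replaces dosed patients who stop before completing Blocks 1 and 2, while the Phase II response denominator is never stated

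*Combined protocol and SAP*

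**What the plan says.** Section 12.1 states: "Patients who discontinue therapy prior to completion of both Block #1 and Block #2 will be replaced". It exempts no reason for stopping. The one case it protects is a patient who has finished both blocks and then leaves treatment for progression; that patient "will still be evaluable for efficacy and will not be replaced". The paragraph continues: "If needed a subgroup of patients receiving all 3 blocks will also be evaluated for response as a secondary population". It then adds: "We expect that the number of patients coming off therapy after only completing block #1 will be minimal". Evaluability for toxicity is set separately, at completion of Block 1. Enrolled patients who cannot begin treatment have their own rule in Section 6.4: "The patient will be replaced to fulfill enrollment requirements".

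The design text counts differently. Stage 1 in Section 12.1 reads "Enroll a total of 13 patients (including all treated at the MTD in Phase I"), and Section 7.2.2 says "an additional 17 patients will be enrolled for a total of 30 patients treated at the MTD". The trial continues with at least 3 responses in 13 and is called promising with 10 in 30. Section 12.3 sets 20% against 40%, with 80% power and a significance level of 0.05, and does not say which patients those rates describe. Section 12.2 estimates response by simple proportions and gives no denominator.

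Under Sections 7.1.5, 7.3, 7.5 and 10.3, a DLT ends treatment for any patient, in Phase II as well as Phase I.

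**The concern.** The replacement rule can act only on patients who have received drug. Many who stop in the first two blocks will have stopped for toxicity or intercurrent illness, and they are unlikely to have responded. If they are taken out of the 13 and the 30 and others put in, the response rate is measured among patients selected by what happened to them after dosing. The extension is uncontrolled, so no comparator arm shares the selection.

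The silence on the denominator matters in its own right. Two analysts, each with a defensible reading of the protocol, could apply the same 3/13 and 10/30 rule to the same data and reach different decisions.

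**Working it through.** **Step 1: the text side by side.**
- Replacement (12.1): any dosed patient who has not completed both blocks, whatever the reason.
- Efficacy evaluability (12.1): affirmed only for two-block completers who progress.
- Named populations (12.1): a toxicity set (Block 1 completed) and an optional secondary response set (all three blocks). No primary response set is named.
- Places to fill (12.1, 7.2.2): patients treated at the MTD.

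The first two items point to a set of two-block completers. The last points to everyone treated. Nothing chooses between them.

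**Step 2: the plan's own figures.** From Section 12.1, n1 = 13 (continue at 3 or more) and n = 30 (success at 10 or more). From Section 12.3, the rates are 20% and 40%. Sidedness is not stated; a one-sided exact test is assumed.

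Go(p) = Σ over x = 3 to 13 of Bin(x; 13, p) × P[Bin(17, p) ≥ 10 − x]

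- Go(0.40) = 0.8051, which agrees with the stated 80% power.
- Go(0.20) = 0.0577, against a stated 0.05. That gap exists with no replacement at all and is a separate matter. It is the baseline here.

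**Step 3: false-go if replaced patients are dropped.** Let d be the fraction of dosed patients replaced, p the response rate in all treated patients and s the response rate in replaced patients. The rate in the retained set is (p − d·s)/(1 − d). The documents give no d, so the values below are assumed. Take p = 0.20 for all treated patients.

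| d (assumed) | retained rate, s = 0 | false-go, s = 0 | retained rate, s = 0.10 | false-go, s = 0.10 |
|---|---|---|---|---|
| 0 | 0.2000 | 0.058 | 0.2000 | 0.058 |
| 3% | 0.20/0.97 = 0.2062 | 0.069 | not shown | not shown |
| 5% | 0.20/0.95 = 0.2105 | 0.077 | 0.195/0.95 = 0.2053 | 0.067 |
| 10% | 0.20/0.90 = 0.2222 | 0.104 | 0.190/0.90 = 0.2111 | 0.079 |

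If 20% was meant for two-block completers, the retained rate is 0.20 by definition and there is no inflation. As an illustration, 10 of 30 (33.3%) becomes 10 of 33 (30.3%) when three replaced patients are counted.

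**Step 4: how often the two readings disagree.** This does not depend on whom 20% describes. Let c be the completer response rate and suppose early stoppers never respond. The first 13 and 30 completers then include every completer among the first 13 and 30 treated. So the chance of go among completers but no-go among all treated is Go(c) − Go(c(1 − d)). At c = 0.30:
- d = 5%: Go(0.30) − Go(0.285) = 0.3944 − 0.3267 = 0.0677
- d = 10%: Go(0.30) − Go(0.27) = 0.3944 − 0.2629 = 0.1315

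If stoppers respond at 10%, simulation (200,000 runs) also gives a few reversals, where counting all treated patients says go and counting completers says no-go: about 0.011 at d = 5% and 0.015 at d = 10%.

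**The case against.** The strongest reply is that the plan says replaced, not removed from the analysis, and that two sections speak of patients treated at the MTD. This stands to a degree. A reader might infer that the protocol openly excludes toxicity stops from the primary analysis. It does not: exclusion is implied by the contrast with evaluable completers and is nowhere stated.

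A second reply is that a two-block-completer set can be inferred and is a legitimate choice for a preliminary, uncontrolled estimate. That is fair, but the plan would have to name the set, say that toxicity stops are left out, and say that 20% and 40% describe completers. It does none of these.

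A third is that the plan expects few such patients. If so, the effect is small: 0.069 at d = 3%. But the statement carries no figure and concerns patients who completed only Block 1, not those who stop within it.

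Four stronger readings are tempting and not supported:
- **That about 20% will be replaced, because the MTD targets a 20% DLT rate.** The DLT window is 28 days, while Block 2 ends on Day 12 (Section 10.2). The prolonged-cytopenia DLTs need at least 29 days. Many Grade 3 non-hematologic events become DLTs only after more than 72 hours. The true DLT rate at the chosen dose may also be below target.
- **That deaths are expressly replaced.** Section 12.1 does not mention death; it falls under the rule only if read as discontinuing therapy.
- **That the two readings can differ in one direction only.** This is true only if early stoppers never respond.
- **That the Revision 9 entry in the Revision History proves a defect.** A change log describes an amendment, and a difference between it and the current text is not an error. The point rests on the current sections alone.

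**Conclusion.** The point holds as an unresolved denominator combined with a replacement rule that has no toxicity exception. It does not show that the primary analysis is biased as planned. Following the implied reading would condition the single-arm decision on post-dosing events. For assumed replaced fractions of 3% to 10%, this moves the false-go chance from 0.058 to between 0.069 and 0.104, provided that 20% describes all treated patients and replaced patients do not respond. The rise is smaller if some of them respond, and there is none if 20% describes completers. Whichever population was meant, roughly 7% (d = 5%) to 13% (d = 10%) of trials with a 30% completer response rate would get a different decision under the two readings, with non-responding stoppers. It should be fixed before Phase II data are seen; confidence is medium because d is assumed and removal is only implied.

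**What to change.** In Section 12.1, for the Phase II efficacy decision:
- Define the primary response set as all patients who received any GTB-3550 at the MTD, including Phase I patients at that dose, in enrolment order.
- Count anyone without a documented response by Day 42 as a non-responder.
- Apply 3/13 and 10/30 to that set, or the adjusted futility rule of Sections 12.1 and 12.3 if more than 13 patients were treated at the MTD in Phase I.
- State that 20% and 40% describe treated patients, and that replacement does not remove anyone from this set.
- Report two-block and three-block completers as sensitivity analyses, with the number of early stops and the reasons.

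The replacement rule should not simply be carried over to Phase I. Section 12.1 ties DLT evaluability to completing Block 1, yet Sections 7.2.1 and 10.3 make inability to complete a block because of treatment-related toxicity a DLT in itself. These must be reconciled so that a patient with a DLT stays in the CRM data. Section 12.1 must also be reconciled with Section 7.3.3 on whether a block cut short for liver tests counts as completed.

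The cost is wording only, with no added enrolment if 20% and 40% describe treated patients. The reported response rate will be somewhat lower. If 40% was meant for completers and early stoppers do not respond, power falls from 0.805 to Go(0.40 × 0.95) = Go(0.38) = 0.740 at d = 5%, or Go(0.40 × 0.90) = Go(0.36) = 0.664 at d = 10%. Both are below the stated 80%, and the plan should say so.

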### **7.1 GTB-3550 TriKE Administration**

Patients receive a single course of GTB-3550 TriKE at their assigned dose as 3 weekly treatment blocks. Each block consists of four consecutive 24 hour

continuous infusions (over approximately 96 hours) of GTB-3550 TriKE followed by a 72 hour break after Block #1 and #2. All treatment is given as an inpatient.

The assigned dose will be calculated on a weight obtained within 5 days prior to or on day of the 1st dose. The dose is not be recalculated for subsequent treatment blocks.

The institutional Investigational Pharmacy will prepare each 24 hour bag for infusion per [Section 9.6](#) based on the patient's assigned GTB-3550 TriKE dose. Each assigned dose will be administered as a 100 mL infusion over 24 hours period at 4.17 mL/hour rate. Note: actual bag volume is 130 ml to allow for the product sample collection before and after infusion.

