#### **7.1.5 Criteria to Continue with GTB-3550 TriKE Block #2 and #3**

A dose limiting toxicity (for any patient, not just dose finding) during the previous block's infusions (defined in [Section 7.2.1](#)) will disqualify a patient from receiving further therapy.

**Disease based treatment decisions:** If after completing Block #1 and Block #2, the patient has clear evidence of disease progression they will be discontinued from study treatment and further treatment with study drug is to be discontinued. Such patients remain fully evaluable for efficacy and toxicity.

To begin a new block, on the day of the planned treatment the patient must:

- not currently meet any disease specific hematologic dose limiting toxicity as defined in [Section 7.2.1](#).
- have an estimated glomerular filtration rate  $\geq 60$  mL/min/1.73 m^2
- have a total bilirubin of  $\leq 1.5$  times the ULN

- have AST and ALT  $\leq$  3 x upper limit of normal, and alkaline phosphatase levels  $\leq$  2.5 x upper limit of normal
- be afebrile (defined as a temperature of  $\leq$  101°F)
- have room air O2 saturation  $\geq$  88%
- have a blood pressure  $\geq$  100/65 mm/Hg
- have no signs or symptoms of infection

If the above criteria is not met, treatment must be delayed for appropriate supportive care and clinical assessment. The study drug may begin the following day, if the above criteria are met and, in the opinion of the clinical provider it is safe to proceed. Otherwise delay 1 week from the planned start and reassess at that time.

Patients unable to begin treatment after a 1 week delay will be permanently discontinued from treatment and followed per [Section 7.6](#).

The start of Block #2 or Block #3 may be delayed for up to 1 week (i.e. start 1 week later than planned) to allow for the resolution of any treatment or non-treatment issues (i.e. URI, UTI, etc.) or for holiday/scheduling issues.

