    - Grade 4 platelet count (<25,000/ $\mu$ L) lasting  $\geq$  29 days from start of cycle in the absence of active MDS/Mast cell disease
    - Any clinically significant bleeding that is not controllable with transfusion support
    - Grade 4 anemia, unexplained by the underlying disease

- Grade 3 infusion related, treatment related reaction including cytokine release syndrome which does not resolve within 72 hours despite best medical management (refer to [Section 10](#) for modified CRS grading)
- Grade 3 or 4 Tumor Lysis Syndrome that does not resolve within 7 days with or without intervention
- Inability to complete at least one block of three 24 hour infusions due to any treatment emergent, treatment related toxicity.

**Maximum Tolerated Dose (MTD)** is defined as the dose level that most closely corresponds to the target DLT rate of 20%.

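### Section 12.1 does not say that a patient whose treatment is stopped by a DLT in Block #1 is DLT-evaluable, counts toward the 30, and is not replaced for dose finding

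*Combined protocol and SAP*

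**What the plan says.** Section 12.1 has carried the evaluability and replacement rules since Revision 9, which the Revision History describes as a change to "add the definition of evaluable and when to replace a patient to complete enrollment". Three of its sentences matter here.

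- Evaluability: "All patients completing Block #1 will be evaluable for DLTs and toxicities".
- Replacement: "Patients who discontinue therapy prior to completion of both Block #1 and Block #2 will be replaced".
- Progression: patients who finish both blocks but "come off treatment for disease progression, will still be evaluable for efficacy and will not be replaced". Section 7.1.5 agrees: "Such patients remain fully evaluable for efficacy and toxicity".

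Elsewhere, a DLT during a block "will disqualify a patient from receiving further therapy" (7.1.5), and 7.5 also ends the course for a DLT-equivalent toxicity. The DLT list in 7.2.1, repeated in 10.3, includes "Inability to complete at least one block of three 24 hour infusions due to any treatment emergent, treatment related toxicity". Section 7.1 describes the block differently: "Each block consists of four consecutive 24 hour" infusions. Phase I enrollment runs until 30 evaluable patients have been accrued (7.2.1). Section 6.4 also provides for replacement, but only of patients who never start treatment.

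**The concern.** A DLT forces a stop, and a stop before the end of Block #2 triggers replacement. A patient stopped by a DLT in Block #1 has not completed Block #1, so is not in the group that 12.1 names as DLT-evaluable. Section 10.3 nevertheless lists the event as one that counts. Nothing in 12.1 says which text governs the CRM data set or the count of 30.

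The Phase I primary objective is the dose with a DLT rate nearest 20%, each cohort of 2 is placed by the updated CRM, and the chosen dose goes into Phase II. If the literal reading were applied, the patients removed would be those with DLTs. The apparent DLT rate would then be too low and the selected dose could exceed the target.

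**Working it through.** **Passages side by side**

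| Situation | 12.1, read literally | 7.2.1, 10.2, 10.3 and CRM text |
|---|---|---|
| DLT stops treatment in Block #1 | Not named as DLT-evaluable; replaced | Listed DLT; 28 days of assessment even after an early stop; cohort enters the update at Day 28 |
| DLT stops treatment in Block #2 | DLT-evaluable (Block #1 completed); also replaced | Listed DLT |
| Progression after Blocks #1 and #2 | Evaluable for efficacy; not replaced | Evaluable for efficacy and toxicity (7.1.5) |

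The first row is the real gap. In the second the event is kept, and the open questions are whether a patient is added and which of them counts toward the 30.

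**Plan's own figure.** The only one involved is the 30 evaluable patients (27 rounded up, 12.3). It is not in dispute, and its formula is only cited.

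**Effect on dose assignment.** Inputs from 12.1: DLT probability at level i is s_i^exp(a), with a ~ N(0, variance 0.5); target 20%; cohorts of 2; no skipping on escalation. The skeleton s is 3, 5, 7, 10, 14, 17, 20%. Placing the 17% of the 5/5/2021 revision at level 6 is my assumption, because the plan calls it an expected true probability. I also assume that all lower levels are 0/2, that the DLTs stop treatment in Block #1, that replacements are DLT-free at the same level, and that estimates plug in the posterior mean of a.

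Worked case, two DLTs at level 5 (100 µg/kg/day):

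- Counted, 2/2: posterior mean of a = −0.313, so 0.14^exp(−0.313) = 23.7%. Level 4 is at 18.6%, closer to 20%. Next level 4.
- Counted and two patients added, 2/4: a = −0.212, giving 20.4%. Next level 5.
- Left out and replaced, 0/2: a = 0.511, giving 3.8%. No skipping limits the move to level 6.

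| DLTs | Counted | Counted, patients added | Left out and replaced |
|---|---|---|---|
| Two at level 4 | 24.3%, next 3 | 20.5%, next 4 | 3.0%, next 5 |
| Two at level 5 | 23.7%, next 4 | 20.4%, next 5 | 3.8%, next 6 |
| Two at level 6 | 22.6%, next 5 | 19.6%, next 6 | 4.1%, next 7 |
| One at level 1 | 18.9%, stay at 1 | depends on estimator | 1.8%, next 2 |

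The percentage is the estimated DLT rate at the level where the DLTs occurred. The next levels shown are the same if the posterior mean probability is used. The exception is one DLT at level 1 with one patient added (1/3): level 2 by plug-in, level 1 by posterior mean.

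A single DLT at level 4, 5 or 6 does not change the next level (5, 6, 7). Only the estimate moves: 14.5% versus 3.0%, 14.8% versus 3.8%, 14.4% versus 4.1%.

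**Reduced increments in 7.2.1.** A DLT also cuts later increases to 50%. From level 5 the printed step (100 to 150) is already 50%, so that result stands. After a DLT at level 4, with a prior of 11 to 13% assumed for 75 µg/kg/day, the three readings still diverge: 25, 50 or 75. At level 1 the cut would make the next level 5 × 1.5 = 7.5, for which no prior is given, so the level 1 result applies to the printed ladder.

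**Effect on the apparent rate.** If a share f of DLT patients were left out, the apparent rate is p(1 − f)/(1 − pf). Setting this to 0.20 gives p = 0.2/(1 − f + 0.2f):

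- f = 0: 0.2/1.00 = 20%
- f = 10%: 0.2/0.92 = 21.7%
- f = 25%: 0.2/0.80 = 25%
- f = 50%: 0.2/0.60 = 33%

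The documents give no timing of DLTs, so f is purely an assumption.

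**The case against.** A reader might infer that the plan discards DLTs. The documents do not support that. The evaluability sentence gives a sufficient condition and does not say that only Block #1 completers qualify. Replacing a patient means enrolling another; no sentence removes the first patient's event from the model. Section 10.3 says the listed events count. A criterion for failing to complete a block would serve no purpose if such patients were left out. Section 10.2 keeps early stoppers under assessment, 12.1 takes its DLT definition from 7.2.1 with no minimum exposure, and 7.2.1 lets a DLT in one patient slow later escalation. All of this stands and makes counting the more natural intention.

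A reader might also infer that progression is the one exception written into the replacement rule, so that DLT stops were knowingly left inside it. That does not follow: the progression sentence covers patients who completed both blocks and were never within the rule.

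The divergences at levels 4 to 6 need two DLTs in a cohort of two, both in Block #1. At the plan's prior rates, two DLTs have probability 0.10² = 1.0%, 0.14² = 2.0% and 0.17² = 2.9%; at a true 20% it is 4%. They are worst cases.

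Finally, the replacement sentence may be meant for efficacy alone, since the next sentence concerns efficacy. The text does not limit it so, and it directly follows the DLT-evaluability sentence. What survives is that no passage says a patient with a Block #1 DLT is evaluable, counts toward the 30, or is not replaced.

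**Conclusion.** The gap is real and should be fixed. Section 12.1 is the operative definition, and its literal reading leaves a patient with a Block #1 DLT outside the evaluable 30 and replaced, against the direction of 7.2.1, 10.2, 10.3 and the CRM text. For a Block #2 DLT only the replacement and the count are unclear.

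The worst case is a two-level difference in the next assignment after two DLTs at level 5 (6 instead of 4), and escalation instead of repeating level 1 after one DLT in the first cohort. These results rest on the skeleton assumption, 0/2 at lower levels, DLT-free replacements and stops in Block #1. They show why the wording matters; they do not predict how the trial will be run, and if DLTs are counted this bias does not arise.

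The three- versus four-infusion mismatch leaves a second group undefined. A Grade 3 infusion reaction during the fourth infusion requires permanent discontinuation (7.1). If it resolves within 72 hours, the patient may have neither a DLT nor a completed Block #1.

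**What to change.** Add to Section 12.1: any treated patient with a Section 7.2.1 DLT is DLT-evaluable whatever the number of infusions or blocks received; enters every CRM update and the lowest-dose stopping rule of 12.4 as a DLT; counts toward the 30; and is not replaced for dose finding. State separately that replacement for efficacy removes no DLT data.

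Reconcile the passages giving three infusions per block (DLT criterion in the Study Schema, 7.2.1 and 10.3) with those giving four (treatment plan). As part of that, settle the dose-finding status of patients stopped in Block #1 by toxicity that is not a DLT. How to treat them is the sponsor's choice and depends on which block definition is meant.

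The cost is one paragraph of protocol wording plus the reconciliation, with no added patients.
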